### 3.7 Economic Analysis

#### Objective

The economic analysis aims to compare the direct medical costs associated with antibiotic therapy and hospital stay between the control and intervention groups in the trial. The goal is to evaluate whether procalcitonin (PCT)-guided de-escalation of antibiotic use reduces the overall economic burden of treatment. A detailed analysis plan on the economic evaluation will be provided separately. Initial components are listed below:

#### 3.7.1 Cost Calculation

##### Antibiotic Therapy Costs

###### Intervention Group:

- Let  $C_{antibiotic,ij}$  be the cost of antibiotic therapy for patient  $i$  using antibiotic  $j$  in the intervention group. The standard maximum retail prices set by the producer will be used in this case.
- Let  $C_{PCT}$  be the cost of the procalcitonin test per patient. The average PCT testing charge set by the diagnostic centers will be used in this calculation.
- Total cost for antibiotic therapy for the intervention group  $C_{antibiotic, intervention}$  is:

---

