## 2. Introduction and study summary

Antimicrobial resistance (AMR) is a global problem, resulting in increased morbidity and mortality from multidrug resistant bacterial infections that are challenging to treat. Low- and middle-income countries (LMICs), like Bangladesh, are disproportionately affected by AMR. Excessive use of antibiotics both inside and outside the hospital is thought to be an important driver of AMR in Bangladesh and other LMICs. Several studies have shown that sequential assessment of serum procalcitonin (PCT) concentrations is an effective and safe strategy to shorten the duration of antibiotic therapy in critically ill patients. In this strategy, a decrease of procalcitonin below a certain threshold prompts the clinician to stop or reduce antibiotic treatment. However, these studies were conducted in high resource settings with standard laboratory PCT testing at considerable costs. We propose to evaluate the use of sequential serum PCT measurement to guide de-escalation of antibiotic therapy in a randomised clinical trial in patients with sepsis in a large tertiary referral hospital in Chattogram, Bangladesh, using low-cost point-of-care quantitative procalcitonin measurements. Main endpoint of the trial will be the difference in antibiotic therapy duration between the study groups. If this study shows that PCT guided de-escalation of antibiotics results in a safe reduction in antibiotic usage, this will be an important strategy to reduce the antibiotic burden in hospitals in Bangladesh and comparable resource-limited settings, as well as other consequences of prolonged antibiotic therapy, including increased costs, prolonged duration of intravenous lines and duration of stay, and microbiota changes.

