### 2.1 Study objectives and endpoints

#### 2.1.1 Primary objective

To assess the **efficacy** of antibiotic de-escalation rules based on daily procalcitonin measurements to reduce the length of antibiotic treatment in hospitalized patients with sepsis in a low-resourced setting.

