#### 2.1.2 Primary endpoint

**Length of antibiotic treatment:** number of days of antibiotic treatment during the study period (till 28 days after hospital discharge). The primary outcome data for participants with recurrent infections will be censored at the time of recurrent infection diagnosis.

---

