### 2.1.3 Secondary objectives and endpoints

- To assess if procalcitonin guided de-escalation reduces antibiotic **consumption** and days of therapy with antibiotics.

- Consumption of antibiotics expressed as the Defined Daily Dosage (DDD)

*Definition of DDD: The basic definition for a defined daily dose is the assumed average maintenance dose per day for a drug used in its main indication in adults. Antibiotic use using the WHO DDD definition ([https://www.whocc.no/atc\\_ddd\\_index/](https://www.whocc.no/atc_ddd_index/)) will be determined for the most frequently prescribed Drugs in Bangladesh*

- Days of therapy with antibiotics (DOT)

Definition of DOT: One DOT represents the administration of a single antibiotic on a given day regardless of the number of doses administered or dosage strength. If a patient receives more than one antibiotic it will be added on with DOT of the first antibiotic. (Dalton et al. 2015)

- Number of days of parenteral antibiotic during hospitalisation period
- Number of days of antibiotic treatment during the hospitalisation period.

- To assess the safety of procalcitonin guided de-escalation of treatment
  - Overall mortality, mortality-associated with recurrent infection, and non-lethal recurrent infections.
- To assess the effect of procalcitonin guided de-escalation on length of hospital stay
  - Duration of hospital stay (ICU/ general ward)
- To determine the spectrum of antimicrobial resistance among bacteria identified in clinical specimens from Bangladeshi patients hospitalized with sepsis
  - Bacterial isolates from blood cultures will be identified, tested for antibiotic susceptibility. In a subset of antibiotic resistant isolates, genetic correlates of resistance will be assessed (A comprehensive microbiological analysis plan is provided in section 3.6).
- To compare the patient care costs between study arms
  - Direct medical costs of prescribed antibiotics, the PCT assay and hospital stay costs.

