### 2.3 Determination of sample size

The sample size calculation is based on the expected difference in mean length of antibiotic treatment between the experimental and control arm. Based on retrospectively collected data from CMCH, the mean length of therapy (LOT) in sepsis patients was 5.2 days with a standard deviation (SD) of 8 days. The SD of the duration of antibiotic prescription in population level was derived by dividing the difference between the maximum and minimum value of LOT that was obtained from the retrospective data by four as one of the rules of thumb. The SD is assumed to be the same in the experimental and the control arms. We hypothesize to have a higher mean number of days of LOT in the control group as compared to the experimental group – i.e 5.2 days in the control group vs. 3.2 days in the experimental group, for an absolute reduction of mean LOT of 2 days. The level of significance was set at 5% (i.e., alpha=0.05). Based on these assumptions and estimating with 80% power, a total of 506 participants are required (i.e., 253 in the experimental arm and 253 in the control arm) to verify the study hypothesis. We anticipate a 5% loss to follow-up and to compensate for this, a total of 532 participants will be enrolled (266 in the experimental arm and 266 in the control arm). The sample size calculations have been performed in R software (version 4.2.1).

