### DDD (Defined Daily Dose)

According to WHO "The DDD is the assumed average maintenance dose per day for a drug used for its main indication in adult"

In the absence of electronic medication management systems, the Defined Daily Dose (DDD) is a valuable metric for assessing drug consumption. The Anatomical Therapeutic Chemical (ATC)/DDD methodology, endorsed by the World Health Organization (WHO), is an internationally recognised standard for evaluating drug usage. Guidelines for calculating DDD can be found on the WHO website [here](#). In this study, we will apply the WHO ATC/DDD methodology to determine DDD, with the aim of producing high-quality, practical, and comparable drug utilisation statistics (2).

Drug utilisation data expressed in DDDs offers an approximate estimate of consumption but does not precisely reflect actual usage. DDDs serve as a standardised unit of measurement, unaffected by factors such as price, currency, packaging size, or strength, allowing researchers to examine trends in drug utilisation and compare usage across different population groups.

To calculate the Defined Daily Dose (DDD) for each antibiotic, use the following steps:

1. **Identify the Route of Administration:** Confirm the administration route (e.g., IV, oral) for each antibiotic dose, as the DDD value varies with the route.
2. **Total Dose Administered:** Sum the total dose of each antibiotic administered per patient, as recorded in the dataset.

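### The procalcitonin cost formula contains no number of tests: read literally, each intervention patient is costed for one test although testing is daily

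*SAP*

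**What the plan says.** SAP section 3.7.1 (Antibiotic Therapy Costs, Intervention Group) lets C_PCT "be the cost of the procalcitonin test per patient. The average PCT testing charge set by the diagnostic centers will be used". The intervention total is the double sum of antibiotic costs over patients i and antibiotics j, plus 266 × C_PCT. Dividing by 266 gives the per-patient figure, which goes into total cost (3.7.2), the cost difference and its t-test (3.7.3), and the absolute and percentage savings (3.7.4).

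The intervention itself is repeated testing. Section 2 proposes to "evaluate the use of sequential serum PCT measurement to guide de-escalation of antibiotic therapy", and section 2.1.1 speaks of "antibiotic de-escalation rules based on daily procalcitonin measurements".

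The result feeds a listed secondary endpoint in section 2.1.3: "Direct medical costs of prescribed antibiotics, the PCT assay and hospital stay costs".

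Section 3.7 describes its contents as initial components and defers a detailed economic plan to a separate document, which was not available for this review.

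**The concern.** Serial testing is what the intervention arm pays for, so the number of tests drives its added cost. The SAP never states that number and never multiplies the charge by it.

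The other two cost items can vary by patient. Hospital cost is a constant day rate times LOS_i. Antibiotic cost is likewise valued only by a unit price, but it carries indices i and j, and the DDD guidance in section 4.1 shows that the quantity exists: "Sum the total dose of each antibiotic administered per patient, as recorded in the dataset". C_PCT has no index, and the SAP mentions no per-patient test count.

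At a given charge, costing one test when the average is higher makes the intervention look cheaper than it was. The error passes unchanged into the cost difference, the t-test and both savings figures. A constant also treats alike patients who died before the intervention started (kept in the ITT set by section 3.3, part A), patients discharged before procalcitonin reached its target (part B), and patients tested for many days.

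**Working it through.** **Inputs**

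- 266 intervention patients (sections 2.3 and 3.7.1). This is the planned enrolment: 506 × 1.05 = 531.3, rounded up to 532, or 266 per arm.
- c, the average charge for one test. Section 3.7.1 names it without an amount.
- k, the mean number of tests per intervention patient. The SAP does not give it, so the values below are assumptions.
- Planned length of therapy: "5.2 days in the control group vs. 3.2 days in the experimental group" (section 2.3).

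**The formula as printed, taking C_PCT = c**

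- Procalcitonin cost for the arm: 266 × c
- Per patient: 266c / 266 = c, whatever testing took place

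**With tests counted**

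- Arm total: c × Σ(tests for patient i) = 266 × k × c
- Per patient: k × c
- Shortfall of the printed formula: 266(k − 1)c in total, (k − 1)c per patient

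The saving is control minus intervention, so it is overstated by (k − 1)c per patient when k > 1, exact at k = 1 and understated when k < 1. The percentage saving is off by 100 × (k − 1)c divided by the mean total cost in the control arm.

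| Assumed k | Counted total | Printed total | Shortfall, total | Shortfall per patient | Share of test cost captured |
|---|---|---|---|---|---|
| 1 | 266c | 266c | 0 | 0 | 100% |
| 2 | 532c | 266c | 266c | 1c | 50% |
| 3.2 | 851.2c | 266c | 585.2c | 2.2c | 31% |
| 5 | 1330c | 266c | 1064c | 4c | 20% |

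The value 3.2 assumes one test on each day of therapy at the planned experimental mean. It is only a marker. Length of therapy is the "number of days of antibiotic treatment during the study period (till 28 days after hospital discharge"), so it includes days at home, and the mean number of tests could be lower.

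**Could untested patients reverse the direction?** If a share p has no test and the others average m tests, then k = (1 − p)m, and k > 1 when p < 1 − 1/m.

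- m = 2: p < 1 − 1/2 = 50%
- m = 3.2: p < 1 − 1/3.2 = 68.75%

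Under these assumed values of m, at least half the arm would have to go untested before the printed formula stopped understating the cost.

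**Effect on the t-test.** Let B_i be the antibiotic plus hospital cost of patient i, and k_i the number of tests.

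- Counted: Var(B_i + c·k_i) = Var(B_i) + c²Var(k_i) + 2c·Cov(B_i, k_i)
- Printed: Var(B_i + constant) = Var(B_i)

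The last two terms of the first line are lost. This holds for any constant, including a correct mean.

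**The case against.** The strongest reply is that the definition says per patient, so multiplying by 266 patients is dimensionally correct. C_PCT may stand for all tests given to one patient. Antibiotics too are valued only by a price, and nobody infers one tablet each. If C_PCT is the arm's mean testing cost over all randomised patients, early deaths and early discharges are averaged in and the mean is unbiased. This stands in part: the one-test result is a literal reading, not the only one. But the sole valuation offered is a testing charge, and no rule turns it into a per-patient total, so two analysts could follow the text and get different answers. The loss of variation in the t-test remains on either reading.

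A second reply is that the detailed economic plan may settle the matter, and that test counts may be specified in the protocol or case report form. That may be so, and it limits the weight of the point. It does not correct a formula that this SAP prints together with its test and savings equations.

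A third reply is that neither c nor k is known, so nothing shows the amount matters against total cost. That stands. The direction also holds only at a given charge. The trial is described as "using low-cost point-of-care quantitative procalcitonin measurements", and if diagnostic-centre charges exceed the cost of that assay, the valuation would push the other way. That is a separate question, which this point does not settle.

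**Conclusion.** The point holds. As printed, the procalcitonin cost is one constant valued at a testing charge, with no test count, in a trial whose intervention is daily testing. On the literal reading the saving per patient is overstated by (k − 1)c when the mean number of tests exceeds one: 1c at k = 2 and 2.2c at k = 3.2, both values of k being assumptions. The monetary size and its share of total cost cannot be derived from the SAP. If C_PCT is a per-patient total, the mean may be correct, but its derivation is not stated and the t-test still omits variation in testing cost.

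This should be corrected before the cost analysis is run. It affects one component of one secondary endpoint and leaves the primary analysis untouched.

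**What to change.** In section 3.7.1, define C_PCT as the charge per test, using the average charge already named there. Replace 266 × C_PCT with the sum over intervention patients of (procalcitonin tests recorded for patient i) × C_PCT, with zero for patients who had no test. Compute total cost for each patient and use those totals in the t-test of section 3.7.3. Carry the same definition into the separate economic plan.

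The cost is one definition and one formula line in the SAP, plus extraction of test counts per patient. The reported savings may become less favourable to the intervention.

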**STATISTICAL ANALYSIS PLAN**

---

$$C_{\text{antibiotic plus PCT, intervention}} = \sum_{i=1}^{266} \sum_{j=1}^n C_{\text{antibiotic}ij} + 266 \times C_{\text{PCT}}$$

- Per patient cost for antibiotic therapy in the intervention group  $\bar{C}_{\text{antibiotic, intervention}}$  is

$$\bar{C}_{\text{antibiotic plus PCT, intervention}} = \frac{C_{\text{antibiotic plus PCT, intervention}}}{266}$$

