**Control group:**

- Let  $C_{\text{antibiotic}ij}$  be the cost of antibiotic therapy for patient  $i$  using antibiotic  $j$  in the intervention group.
- Total cost for antibiotic therapy for the control group  $C_{\text{antibiotic, control}}$  is:

$$C_{\text{antibiotic, control}} = \sum_{i=1}^{266} \sum_{j=1}^n C_{\text{antibiotic}ij}$$

- Per patient cost for antibiotic therapy in the control group  $\bar{C}_{\text{antibiotic, control}}$  is

$$\bar{C}_{\text{antibiotic, control}} = \frac{C_{\text{antibiotic, control}}}{266}$$

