**Intervention Group:**

- Total hospital stay cost for the intervention group  $C_{\text{hospital, intervention}}$  is

$$C_{\text{hospital, intervention}} = \sum_{i=1}^{266} LOS_i \times C_{\text{inpatient\_day}}$$

- Per patient hospital stay cost in the intervention group  $\bar{C}_{\text{hospitl, intervention}}$  is

$$\bar{C}_{\text{hospital, intervention}} = \frac{C_{\text{hospital, intervention}}}{266}$$

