**STATISTICAL ANALYSIS PLAN**

---

- Per patient hospital stay cost in the control group  $\bar{C}_{\text{hospital, control}}$  is

$$\bar{C}_{\text{hospital, control}} = \frac{C_{\text{hospital, control}}}{266}$$

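### The per-patient cost formulas in SAP 3.7.1 fix planned enrolment (266 per arm) as sum limit, PCT multiplier and divisor; they should use the number of patients actually costed (minor).

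*SAP*

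**What the plan says.** Section 3.7.1 gives four per-patient cost formulas. Each takes an arm total and divides by the literal number 266. The formula code reads:

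- antibiotic plus PCT cost, intervention arm: "antibiotic plus PCT, intervention}}}{266"
- antibiotic cost, control arm: "antibiotic, control}}}{266"
- hospital stay cost, intervention arm: "hospital, intervention}}}{266"
- hospital stay cost, control arm: "hospital, control}}}{266"

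The totals above these divisors are sums from i = 1 to 266, and PCT enters the intervention total as 266 times the PCT cost per patient. Section 3.7.2 adds the means within each arm, 3.7.3 takes the difference between arms and calls for a t-test, and 3.7.4 turns that difference into an absolute and a percentage saving.

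The origin of 266 is section 2.3. The calculation there ends with "a total of 506 participants are required (i.e., 253 in the experimental arm and 253 in the control arm"), and then, after an allowance for 5% loss to follow-up, "a total of 532 participants will be enrolled (266 in the experimental arm and 266 in the control arm").

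Section 3.7 says that a detailed economic plan will come separately and that what follows are its initial components. Section 2.1.3 lists the comparison of patient care costs as a secondary objective.

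**The concern.** A mean needs the number of patients who contributed to it. Here the number is set in advance at the recruitment target, and nothing in the SAP replaces it by the number randomised or costed. Elsewhere the SAP leaves the analysed number open: section 1.1 ties inclusion in key secondary analyses to complete data collection, and Table 2 heads each arm with an unfilled N.

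The formulas are therefore right only when an arm has exactly 266 costed patients. Otherwise the mean costs, the saving and the percentage saving depend on how many patients were costed as well as on what they cost. If the two arms differ in that number, part of the reported saving, or its sign, can come from the count alone. The stated purpose of the section is to judge whether PCT guidance lowers the economic burden, so this is the quantity a reader would take away.

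**Working it through.** **1. Where 266 comes from.** Inputs from section 2.3: difference 2 days, SD 8 days, alpha 0.05 (taken as two-sided), power 80%. The normal approximation gives 252 per arm. The t-test version gives 252.13, rounded up to 253, the SAP's figure. Allowing for 5% loss: 253 × 1.05 = 265.65, rounded up to 266; 253/0.95 = 266.3. So 266 reproduces as planned enrolment per arm.

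**2. What the formulas return for another n.** Let A and H be the true mean antibiotic and hospital costs in an arm, and P the PCT cost per patient. Suppose n patients are costed, n is below 266, and those n have the arm's true mean costs. Followed literally:

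- control mean = (n_C/266) × (A_C + H_C)
- intervention mean = (n_I/266) × (A_I + H_I) + 266 × P/266 = (n_I/266) × (A_I + H_I) + P

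The antibiotic and hospital parts shrink by n/266; the PCT part does not. At n = 253 (266 less 5% is 252.7) the factor is 253/266 = 0.951, so those parts are 4.9% too low. If n exceeds 266, the sums stop at 266 and omit the remaining patients.

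**3. Equal shortfall.** The SAP gives no unit costs, so these are assumed: control 52 + 68 = 120; intervention 32 + 58 = 90, plus PCT 10, giving 100. The true saving is 20, or 16.7%. With 253 costed in each arm:

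- control: 120 × 0.951 = 114.14
- intervention: 90 × 0.951 + 10 = 95.60
- saving: 18.53, or 16.2%

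The percentage is off by (P/control mean) × (266/n − 1) = (10/120) × 0.0514 = 0.43 points, and would be exact if P were zero. The means and the absolute saving are still wrong.

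**4. Unequal numbers, same assumed costs.**

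| PCT cost | True saving | Costed, intervention / control | Reported saving |
|---|---|---|---|
| 10 | 20 (16.7%) | 253 / 266 | 24.40 (20.3%) |
| 10 | 20 (16.7%) | 266 / 253 | 14.14 (12.4%) |
| 30 | 0 | 253 / 266 | +4.40 (+3.7%) |
| 30 | 0 | 266 / 253 | −5.86 (−5.1%) |

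**5. Spurious saving without unit costs.** Let both arms have the same true total cost and let p be the PCT share of the intervention cost. With an assumed 245 intervention and 261 control patients costed:

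spurious saving = 1 − [245(1 − p) + 266p]/261 = (16 − 21p)/261

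- p = 0: 6.1%
- p = 0.10: 13.9/261 = 5.3%
- p = 0.25: 10.75/261 = 4.1%
- p = 0.50: 5.5/261 = 2.1%

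Thus 6.1% is the ceiling for this split, reached only if PCT costs nothing. Reversing the split would count against the intervention.

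**6. Agreement with the rest of the SAP.** Hospital cost is length of stay times one constant, so mean hospital cost should equal the mean stay in Table 2 times that constant. With a divisor of 266 and fewer patients, it does not. Likewise, the t-test in 3.7.3 needs patient-level costs and uses the patients present, so the difference it tests need not equal the saving reported in 3.7.4.

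**The case against.** The strongest reply is that 266 is a placeholder. Sum limit, PCT multiplier and divisor all carry the same number, so each formula is a proper mean at the planned size. Software running the t-test would use the real n, and the section itself defers to a fuller economic plan that is not before us. This stands as a reason to rate the point low. It does not correct the formulas, which are the only estimators the SAP states for a listed secondary objective and could be carried over unchanged.

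Four stronger readings are tempting, and the document does not support them.

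- *About 253 per arm will be costed.* The 5% in section 2.3 is loss to follow-up. Section 3.3 keeps patients without 28-day data in the ITT analysis, censored at the last day of follow-up, and uses the last observed outcome for transfers and departures against advice. Stay cost is known at discharge. The costed number may well be nearer 266.
- *Every mean is 4.9% too low at 253.* The PCT term does not scale, so the intervention total falls by less.
- *Missing cost data always look like savings.* With an equal shortfall and a true saving in the non-PCT costs, the absolute saving is understated; with unequal numbers the error can go either way.
- *The SAP scores missing costs as zero.* It gives no such rule. Zero is what the literal divisor implies when a patient is absent from the sum, and section 1.1 points instead to analysing patients with complete data.

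Large differences in the numbers randomised are also not to be presumed: allocation is 1:1 in blocks, although block sizes are not given. Unequal completeness of cost data is the more plausible route, and its extent is unknown.

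**Conclusion.** The point holds as a minor one. Section 3.7.1 writes planned enrolment where the number of costed patients belongs. The size of the error depends on counts not yet known: none at exactly 266 costed per arm, 4.9% on antibiotic and hospital means at an illustrative 253, and little effect on the percentage saving if both arms fall short equally. If the arms differ, the count alone can create or hide a saving. For the assumed 245 versus 261 that spurious saving is 6.1% at most, and 5.3% or 4.1% if PCT is 10% or 25% of intervention cost.

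These figures assume that the formulas are followed literally and that costed patients have their arm's true mean cost. The unit costs and the unequal counts are illustrations, not figures from the SAP. The primary outcome is not affected.

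**What to change.** In section 3.7.1, replace 266 by n_I and n_C, the actual number of patients in each arm's ITT cost analysis, in all three places: the sums, the PCT multiplier and the divisors. Define a patient-level total cost C_i (antibiotics, PCT where applicable, and stay) and take each arm mean over those patients. State how missing components are handled, by imputation or by reporting the number missing per arm, so that a missing component does not count as zero. In 3.7.3 and 3.7.4, report as the saving the same mean difference that the t-test uses, with its 95% confidence interval. Carry the same definitions into the separate economic plan.

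The cost is a change of symbols and a few sentences. No extra data or patients are needed.
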